This study is a randomized controlled trial with 4 study arms. The total number of initially identified eligible patients who can be contacted via both mail and phone will be divided by 7 to estimate the number of unique patients contacted across 7 sequential waves of outreach occurring from May through November 2023. At each wave, a random subset of 1/7th of the total will be randomized to arms, with slightly larger or smaller subsets selected over time if needed, to compensate for patients becoming newly eligible or ineligible over time (e.g., due to records of completed mammograms prior to the outreach date). Furthermore, a maximum of 300 live calls can be fielded per month, so randomization to the live call arm will be restricted to 300 whenever there are more than 1,200 patients to randomize in a given wave. Auto-dialer messages and live calls will be rolled out across each month, whereas postcards and letters will both be sent in two rounds per month, two weeks apart.

Methods

Female GHP members ages 51 through 74 who are overdue for an annual mammogram will be included in the study. Inclusion and exclusion criteria are largely determined by Healthcare Effectiveness Data and Information Set (HEDIS) guidelines developed by the National Committee for Quality Assurance (NCQA) to assess breast

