cancer screening. Included in the intervention are women between the ages of 52 and 74, as of December 31, 2023. Excluded are women who have had a mammogram (screening, diagnostic, film, digital, or digital breast tomosynthesis) claim between October 1, 2021 and the monthly data pull preceding each monthly wave of outreach, as well as women who have not been continuously enrolled with GHP during that timeframe—i.e., they have had a gap in enrollment of greater than 45 days (or 1 month, for Medicaid beneficiaries) in a given calendar year, or any gap in enrollment between October 1 and the data pull for outreach. Also excluded are GHP members in hospice, using hospice services, or receiving palliative care in 2023. Excluded are Medicare members 66 years of age or above as of the date of the data pull for outreach who are either: (1) enrolled in an Institutional SNP any time during 2023, (2) living long-term in an institution during 2023, or (3) 66 years of age or above as of December 31, 2023 with both frailty and advanced illness (as defined by 1+ claim/encounter for frailty in 2023 and any of the following during 2022 or 2023: 2+ visits with a diagnosis of advanced illness, 1+ acute inpatient encounter with a diagnosis of advanced illness, 1+ acute inpatient discharge with advanced illness diagnosis, or a dispensed dementia medication). Finally, excluded are patients who had a bilateral mastectomy at any time before the data pull for outreach: bilateral mastectomy, unilateral mastectomy with a bilateral modifier, history of bilateral mastectomy, or any combination of codes indicating mastectomy on both left and right side. Mammogram screening evidence comes from GHP claims data, as well as Geisinger electronic health record data and St. Luke's University Health Network, WellSpan Health, PrimeMed Medical Group, Family Practice Center, and Equipt Health data, with GHP claims data trumping other sources except where claims are not on file. The intervention began on May 10, 2023.

At each wave, a random subset (as described above) of currently eligible patients will be randomized to all four of the following study arms:

1. Current **standard postcard** encouraging patients to schedule their mammograms and to contact Geisinger for help doing so.
2. **Formal letter** telling patients that they are overdue and including contact information as above
3. **Auto-dialer** voice message allowing patients to respond to schedule

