4. **Live call** from a GHP care gaps coordinator helping patients schedule while speaking with them.

The remaining patients will serve as contemporaneous controls for patients in the other arms, during the span of time prior to which they are included in an active outreach arm. The controls will include patients eligible for outreach at the time the comparison patients are randomized to the corresponding active arms; they will exclude patients who become eligible at a later date. For example, controls for patients in wave 2 will consist primarily of patients assigned to wave 6, excluding those wave 6 patients who will not have been eligible for outreach at the time of the wave 2 rollout. Additionally, to account for patients who are eligible initially but become ineligible over time, those patients will be randomized to control groups as available. In the example above, a random subset of patients who become ineligible prior to the rollout of other waves will be added to the wave 2 control group.

Finally, for analysis, given that control patients do not have an intervention send date, the starting date will be randomly chosen for each to match one of the treatment arms' send dates.

Power Analysis

With 17,640 patients, we would have 80% power to detect a 2.5% absolute increase in mammograms with two-tailed alpha of .05, between each among standard postcard, letter, and auto-dialer arms, and live calls, assuming a 13.1% baseline incidence of mammograms completed within 180 days. The detectable increase becomes 1.8% when comparing across no-outreach controls and each among standard postcard, letter, and auto-dialer arms, or 3.0% across controls and live calls, assuming an 8.9% mammogram incidence within 120 days. The outcome duration varies according to the availability of appropriate comparator samples. The target effect size and number of patients are informed by practical considerations regarding the anticipated number of eligible women in 2023, the acceptable duration of the intervention (approximately 7 months), the acceptable delay between intervention and outcome being recorded, and effects that seem achievable and useful if achieved.

Project Status

Outreach has begun, as of May 10, 2023 (IVR and live calls) and May 12, 2023 (postcards and letters). No outcome data have been accessed as of the time this file was posted.

Statistical Analysis Plan

Planned Analyses

Primary Outcome: Mammogram completed

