The outcome is determined according to HEDIS criteria and based on a combination of GHP claims data and other sources. The time frames vary according to the availability of appropriate comparator samples. Time frames are specified for each of the analyses below.

Question 1: Does calling people increase mammogram completions relative to other modalities of outreach?

We will test the hypothesis that live calls increase the probability of mammogram completions within 180 days of outreach, relative to other modalities.

Analysis 1 (Confirmatory): Time Frame: In the 180 days following the outreach

We will run an OLS regression including a categorical predictor variable coding for experimental arm (0 = live call, 1 = standard postcard, 2 = formal letter, 3 = auto-dialer). This analysis will include all enrolled patients.

Question 2: Do different modalities of outreach increase mammogram completions relative to no outreach?

We will test the hypothesis that each of the individual modalities increases the probability of mammogram completions within 120 days of outreach, relative to passive control groups.

Analysis 2.1 (Confirmatory): Time Frame: In the 120 days following the outreach

We will run an OLS regression including a categorical predictor variable coding for experimental arm (0 = passive control, 1 = standard postcard, 2 = formal letter, 3 = auto-dialer, 4 = live call). This analysis will include patients in the first 3 waves of active outreach, along with a passive control group consisting of the contemporaneous 120 days of the last 3 waves of outreach, during which outreach will not yet have occurred for those patients.

Other Pre-specified Outcomes

We will run the analyses described above on the following additional outcomes:

1. Mammogram completed – namely, do different modalities of outreach increase mammogram completions relative to each other? We will test whether individual modalities are differentially effective in increasing the probability of mammogram completions within 180 days of outreach, relative to each other (for those modalities not already compared by the analyses above).
[Time Frame: In the 180 days following the outreach]

We will run an OLS regression including a categorical predictor variable coding for experimental arm (0 = standard postcard, 1 = formal letter, 2 = auto-dialer), as well as a separate OLS regression (0 = formal letter, 1 = auto-dialer). This analysis will include patients in all 7 waves of outreach.

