2. Breast malignancy risk detected

High risk of malignancy, among patients visiting Geisinger clinics and, as available, outside Geisinger (yes/no)

[Time Frame: In the 210 days following the outreach]

3. Mammogram appointment scheduled

Appointment scheduled for mammogram, among patients visiting Geisinger clinics (yes/no)

[Time Frame: In the 30 days following the outreach]

Covariates

An interim call to action—calling or speaking with GHP for help with scheduling—may not be as helpful for patients typically seeking care at non-Geisinger clinics as those going to Geisinger health system clinics. Also, we may not get data on mammogram completions as reliably from outside the Geisinger system. Therefore, all the regressions described above will also explore including as a covariate and interaction term whether or not the patient has an attributed Geisinger PCP.

Analysis Notes

Recent work suggests that OLS regressions are appropriate in randomized experiments with binary outcome variables such as ours (Gomila, 2021).

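### The confirmatory OLS models have no term for randomisation wave and no stated standard-error type, although the 300-call cap ties the live-call share to wave size

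*Combined protocol and SAP*

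**What the plan says.** Methods describes randomisation wave by wave: "At each wave, a random subset (as described above) of currently eligible patients will be randomized to all four of the following study arms". Design adds two rules that affect allocation. Wave sizes can move, "with slightly larger or smaller subsets selected over time if needed", and "randomization to the live call arm will be restricted to 300 whenever there are more than 1,200 patients to randomize in a given wave".

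For Analysis 2.1, Methods ties controls to particular active waves. In its example, controls for wave 2 come mainly from wave 6, "excluding those wave 6 patients who will not have been eligible for outreach at the time of the wave 2 rollout". A random subset of patients who later become ineligible is then added.

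The model statement for Analysis 1 reads "We will run an OLS regression including a categorical predictor variable coding for experimental arm (0 = live call", followed by the codes for the other three arms. Analysis 2.1 uses the same model with passive control as the reference. Arm is the only stated predictor in both. Under Covariates, the regressions "will also explore including as a covariate and interaction term whether or not the patient has an attributed Geisinger PCP". That term is exploratory and does not represent wave. Analysis Notes says that "OLS regressions are appropriate in randomized experiments with binary outcome variables such as ours", but does not say whether standard errors will be classical or heteroskedasticity-robust.

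**The concern.** Wave is a randomisation stratum, and the cap means its allocation ratio need not be constant. A capped wave contributes 300 live calls whatever its size, while the other three arms absorb the rest. Larger waves therefore weigh more in the postcard, letter and auto-dialer means than in the live-call mean. If the baseline mammogram rate also differs between waves, an arm-only comparison mixes the wave difference into the live-call effect. Drift in rates is plausible: waves run from May to November, and each draws on patients still unscreened at that point.

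Analysis 2.1 has a parallel gap. Excluding not-yet-eligible controls and adding later-ineligible ones can make the control-to-active ratio differ between wave pairs, and the model has no term for the pairing.

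The standard-error gap does not depend on wave drift. With a binary outcome and unequal arms, classical OLS applies one pooled variance to all arms. If live calls raise the rate, the smallest arm has the largest variance, and pooling understates the live-call standard error.

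Both points leave the analyst a choice in a confirmatory test.

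**Working it through.** **Inputs.** Power Analysis gives N = 17,640, baselines of 13.1% (180 days) and 8.9% (120 days), and target differences of 2.5, 1.8 and 3.0 points. Design gives seven waves and the cap. I assume the three uncapped arms share the remainder equally.

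- Per wave: 17,640/7 = 2,520.
- Live call: 300 × 7 = 2,100.
- Each other arm: (2,520 − 300)/3 = 740 per wave, × 7 = 5,180.
- Analysis 2.1 (three active waves, three control waves): 900 live, 2,220 per other arm, 7,560 controls.

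**The plan's own figure.** The plan states: "With 17,640 patients, we would have 80% power to detect a 2.5% absolute increase in mammograms with two-tailed alpha of .05". A pooled-variance z test of 15.6% (n = 2,100) v 13.1% (n = 5,180) gives 79.3%, so these arm sizes reproduce it. Live call v control at 3.0 points gives 81.3%, which also reproduces. The 1.8-point figure gives only 71.9% with three active waves; that is a separate matter, and 1.8 is used below only as an assumed effect.

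**Live-call share.** 300/2,268 = 13.2% (−10%); 300/2,520 = 11.9% (planned); 300/2,772 = 10.8% (+10%).

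**Bias in Analysis 1.** Bias = wave rates weighted by live counts (equal, 300 each) minus wave rates weighted by (size − 300)/3. The documents give no wave-specific rates, so linear trends around 2,520 and 13.1% are assumed.

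Example, sizes ±10% and rates ±3 points in the same direction: each other arm has 656, 684, 712, 740, 768, 796 and 824 patients (total 5,180), with rate deviations −3 to +3. The live-weighted deviation is 0. The other-arm deviation is (3×168 + 2×112 + 1×56)/5,180 = 784/5,180 = 0.151. The live-call effect is understated by 0.151 points; with opposed trends it is overstated by the same amount.

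| Size trend | Rate trend (points) | Bias (points, either sign) |
|---|---|---|
| none | any | 0 |
| ±5% | ±2 | 0.050 |
| ±5% | ±3 | 0.076 |
| ±10% | ±2 | 0.101 |
| ±10% | ±3 | 0.151 |
| ±20% | ±3 | 0.303 |

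The null standard error is √[0.131 × 0.869 × (1/2,100 + 1/5,180)] = 0.00873. A 0.151-point shift is 0.17 of that and moves the two-sided 5% error to 5.3%.

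**Bias in Analysis 2.1.** With equal active waves, control counts 2,520 × (1−d, 1, 1+d) and pair rates −r, 0, +r, the bias is 2dr/3. For d = 5% this is 0.033 (r = 1 point) and 0.067 (r = 2); for d = 10%, 0.067 and 0.133. The targets are 1.8 and 3.0 points.

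**Classical standard errors.** Classical SE = √[s²(1/nᵢ + 1/nⱼ)], with s² the size-weighted mean of p(1−p) over all arms. True SE = √[pᵢqᵢ/nᵢ + pⱼqⱼ/nⱼ]. Coverage = 2Φ(1.96 × ratio) − 1.

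Live call v postcard: s² = (2,100 × 0.13166 + 15,540 × 0.11384)/17,640 = 0.11596. Classical SE is 0.00881 and true SE 0.00920.

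| Contrast | Scenario | Classical/true SE | Coverage |
|---|---|---|---|
| Live v postcard | live +2.5, other arms at baseline | 0.957 | 93.9% |
| Live v control | live +3.0, others +1.8 | 0.932 | 93.2% |
| Live v control | live +3.0, others 0 | 0.898 | 92.2% |
| Postcard v control | live +3.0, others +1.8 | 0.981 | 94.6% |
| Any | no effect in any arm | 1.000 | 95% |
| Live v control | only the others work (+1.8) | 1.039 | above 95% |

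**Simulation of the remedy** (2,000 runs, sizes ±10%, rates ±3 points). With a true effect of 2.5 points, the arm-only model averaged 2.36 with classical coverage of 93.4%; wave terms with HC2 averaged 2.51 with coverage of 94.7%. With no true effect the means were −0.15 and 0.00. The empirical SD was 0.929 points with and without wave terms.

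**The case against.** The strongest reply is that the stated design produces no bias. Design aims for equal sevenths, allows only small adjustments if needed, and nowhere says that sizes will trend. The tabulated biases also assume that size and rate move together in straight lines over seven waves, which is the worst alignment. If the ±10% sizes and ±3-point rates are paired in every possible order, the mean absolute bias is 0.05 points and 0.15 is the maximum, against a standard error of about 0.9. A ±3-point trend means baselines running from 10.1% to 16.1%, which nothing in the documents supports. For Analysis 2.1, the control counts and pair rates are assumed, and the top-up with later-ineligible patients is not modelled. Contemporaneous controls with matched start dates already deal with part of the calendar-time problem.

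On standard errors, the plan does not say it will use classical ones. Even if it did, they are exact with no effect in any arm and conservative if only the other arms work. The 92.2% figure needs live calls to work and every other modality to do nothing.

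All of this stands as a limit on size. None of it supplies the missing wave term or standard-error type, or gives a reason to leave them open. The objection is also right that robust errors have a price in power, and that offering two robust variants would leave a choice open; the fix deals with both.

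**Conclusion.** The concern holds. The confirmatory models do not reflect the groups within which patients are randomised, and the standard-error type is unstated. The consequence is small and conditional. Bias is zero with equal waves and about 0.05 to 0.15 points in Analysis 1 under the assumed aligned trends. It reaches 0.30 only at ±20% wave sizes, which is more variation than the plan foresees. In Analysis 2.1 it is 0.03 to 0.13 points under assumed imbalance. If classical errors are used, under-coverage at the design effects is about 1 to 3 percentage points for live-call contrasts. No confirmatory conclusion is shown to be likely to change. The change is worth making because it costs little, and because the plan says no outcome data had been accessed when it was posted, so on the documents both choices could be settled without sight of results. Confidence is medium, since wave-specific sizes and rates are not in the documents.

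**What to change.** - **Analysis 1:** add indicators for the seven waves (six degrees of freedom).
- **Analysis 2.1:** add wave-pair indicators, coding each control to the active wave it serves. Methods gives the pair 2/6; by the same spacing the others would be 1/5 and 3/7, which the SAP should confirm.
- **All OLS models:** state heteroskedasticity-robust standard errors and name one variant. HC2 is suitable; HC3 would be nearly identical with arms this large.
- **Postcard, letter and auto-dialer comparisons:** wave indicators are optional, because the cap does not alter the shares among these arms.

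The cost is SAP wording and about one line of code per model. Wave is already recorded to run the design, and the simulation showed no loss of precision from the wave terms. Robust errors are slightly larger for live calls when live calls work. For 15.6% v 13.1%, power is Φ[(0.025 − 1.96 × 0.00881)/0.00920] = 80.0% with classical errors and Φ[0.025/0.00920 − 1.96] = 77.5% with robust ones. The SAP should state this beside its 80% claim.

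### Analysis 2.1 as planned has about 70% power, not 80%, for the stated 1.8-point increase over no outreach; the detectable increase is about 2.0 points, and unused waves 4-7 could support a supplementary estimate.

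*Combined protocol and SAP*

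**What the plan says.** The Power Analysis section opens with the comparison of live calls with the other modalities: "With 17,640 patients, we would have 80% power to detect a 2.5% absolute increase in mammograms with two-tailed alpha of .05". For the no-outreach comparison at 120 days, with an 8.9% control rate, it continues: "The detectable increase becomes 1.8% when comparing across no-outreach controls and each among standard postcard, letter, and auto-dialer arms", and gives 3.0 points for live calls.

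The Design section fixes the counts. The eligible total is "divided by 7 to estimate the number of unique patients contacted across 7 sequential waves of outreach", and "randomization to the live call arm will be restricted to 300 whenever there are more than 1,200 patients to randomize in a given wave". Under Methods, at each wave a random subset of "currently eligible patients will be randomized to all four of the following study arms", so waves 4-7 are randomised in the same way as waves 1-3.

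Analysis 2.1 is labelled confirmatory. It is an OLS regression on a five-level arm factor, with no wave term listed. On the active side: "This analysis will include patients in the first 3 waves of active outreach, along with a passive control group". The control group is described as "consisting of the contemporaneous 120 days of the last 3 waves of outreach, during which outreach will not yet have occurred for those patients". Active follow-up from waves 4-7 therefore plays no part. Women in waves 5-7 enter only as controls, before their outreach, and wave 4 does not enter at all. Analysis 1, on 180-day outcomes, has no such restriction: "This analysis will include all enrolled patients".

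**The concern.** Whether any modality beats no outreach is one of the study's primary aims, and the Power Analysis promises 80% power for it at a stated effect. If the three-wave analysis does not deliver that, a true effect of 1.8 points would be missed more often than the plan says, and a null result would be read as stronger evidence than it is.

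The plan also leaves information unused. About 10,080 of the 17,640 women (4 × 2,520) fall in waves 4-7. They are randomised among the same four arms, and their 120-day outcomes will exist because Analysis 1 follows everyone to 180 days. They cannot show what happens without outreach, but they do show how the modalities differ from one another, and that is part of every arm-versus-control estimate.

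**Working it through.** **Inputs.** Total 17,640, 7 waves, two-tailed alpha 0.05, 8.9% control rate at 120 days and 13.1% baseline at 180 days (Power Analysis and Design); 300 live calls per wave (Design). Assumed: equal waves, an equal split of the non-live patients, and one full wave of controls for each of waves 1-3.

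- Per wave: 17,640/7 = 2,520, with 300 live calls and (2,520 − 300)/3 = 740 in each other arm.
- Waves 1-3: 3 × 740 = 2,220 per postcard, letter or auto-dialer arm; 3 × 300 = 900 live calls; 3 × 2,520 = 7,560 controls.
- All 7 waves: 5,180 per postcard, letter or auto-dialer arm; 2,100 live calls.

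**The plan's own figures.** Power = Φ[(δ − 1.96·s0)/s1], where s0 is the standard error from the pooled proportion and s1 the standard error from the two separate proportions.

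| Comparison | n | Rates | s0 | s1 | Power |
|---|---|---|---|---|---|
| Live v other modality, 2.5 points | 2,100 v 5,180 | 15.6% v 13.1% | 0.00893 | 0.00920 | 79% |
| Live v control, 3.0 points | 900 v 7,560 | 11.9% v 8.9% | 0.01020 | 0.01128 | 81% |
| Postcard, letter or auto-dialer v control, 1.8 points | 2,220 v 7,560 | 10.7% v 8.9% | 0.00701 | 0.00733 | **72%** |

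For the last row: (0.018 − 1.96 × 0.00701)/0.00733 = 0.58, and Φ(0.58) = 0.72. With s1 throughout: 0.018/0.00733 − 1.96 = 0.49, or 69%. At 2.0 points the first formula gives 80%.

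The first two rows reproduce, or nearly so, which supports the derived arm sizes. The 1.8-point row does not. Attempts to rescue it:

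- 10,080 controls: 74%.
- A one-sided test: 81%. This contradicts the stated two-tailed alpha and would put live-call power at 3.0 points at about 88%, since (0.030 − 1.645 × 0.01020)/0.01128 = 1.17.
- Four active waves: 80%. This contradicts Analysis 2.1 and would give live calls 89% at 3.0 points.

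**What waves 4-7 could add.** Take OLS with wave indicators and a common set of modality effects. In units of the outcome variance:

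- Waves 1-3 only: 1/n + 1/7,560, with n = 2,220 or 900.
- All active waves: 2/7,560 + (3/7)(1/n − 1/7,560). The first term is the average active arm against control, from waves 1-3. The second is that arm against the average active arm, from all 7 waves.

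| Arm | Waves 1-3 | All waves | Variance cut | 80% detectable increase |
|---|---|---|---|---|
| Postcard, letter, auto-dialer | 0.000583 | 0.000401 | 31% | 2.0 × √(0.401/0.583) ≈ 1.7 points |
| Live call | 0.001243 | 0.000684 | 45% | 2.95 × √(0.684/1.243) ≈ 2.2 points |

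With control numbers between 20% lower and 10% higher, the cuts are 30-32% and 44-45%. With late waves 10-20% smaller they are 28-30% and 41-43%.

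**Cost if modality differences are not constant.** A 1-point change in one modality after wave 3 shifts its estimate by (4/7)(1 − share of wave):

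- Postcard: (4/7)(1 − 740/2,520) = 0.40 points.
- Live call: (4/7)(1 − 300/2,520) = 0.50 points.

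With outcome variance 0.089 × 0.911, the postcard standard error falls from 0.69 to 0.57 points. Mean squared error for the waves 1-3 effect becomes 0.325 + 0.40² ≈ 0.488, against 0.472 as planned, which is slightly worse. For live calls the standard error falls from 1.00 to 0.74 points, and the model still gains until the change reaches about 1.3 points. A test of arm by period (waves 1-3 v 4-7) would detect a 1-point change with only about 18% power (postcard) or 12% (live call).

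**The case against.** A reader might infer that leaving out waves 4-7 is an error and that the confirmatory model should be replaced. The documents do not support that. The protocol builds this question on contemporaneous controls, and only waves 1-3 have controls free of outreach for 120 days. The restriction gives a direct, concurrent, randomised comparison. It costs efficiency but brings in no bias and contradicts nothing else in the plan.

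A reader might also infer that constant modality differences are harmless to assume because Analysis 1 pools all waves. Analysis 1 does not need the assumption: with concurrent randomisation in similar ratios, pooling estimates an average difference even if effects vary. The all-wave model for Question 2 does need it. There is some reason for doubt, since women who complete a mammogram leave the pool before each later wave and others become eligible, so later waves may respond differently.

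Nor is the no-outreach question the plan's least precise comparison in general. That holds only for live calls (3.0 points), which already meet their target. For the other three arms, even the corrected 2.0 points is smaller than the 2.5 points of Analysis 1.

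These objections stand. They remove the case for changing the confirmatory analysis. They do not touch the shortfall at 1.8 points, and they leave room for the all-wave model as a supplement.

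**Conclusion.** The point holds as a misstated detectable difference together with a missed supplementary analysis. Under the counts the design implies, Analysis 2.1 has about 69-72% power at 1.8 points for postcard, letter and auto-dialer, and about 2.0 points is detectable at 80%. This rests on equal waves, an equal split of non-live patients and about 7,560 controls; raising the controls to 10,080 does not close the gap. The live-call figure is sound.

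The 31% and 45% variance reductions are real but conditional on modality differences being the same in all waves. Changes over time that affect all modalities equally are absorbed by the wave terms; changes in one modality relative to the others are not. The gain also depends on those terms being fitted. Adding waves 4-7 to the arm-only model would appear to cut variance by 44% and 51%, but it would set late active patients against early controls and confound arm with calendar time.

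**What to change.** 1. In the Power Analysis, restate the postcard, letter and auto-dialer figure for Analysis 2.1 as about 2.0 points, and give the arm and control counts behind it.
2. Keep the concurrent waves 1-3 comparison as the confirmatory analysis.
3. Pre-specify a supplementary model on the 120-day outcomes of active patients in all 7 waves plus the waves 1-3 controls. Include the five-level arm factor and wave indicators, with standard errors clustered on the woman, because women in waves 5-7 contribute a control period and a later active period.
4. State its assumption beside it: waves 4-7 inform only modality-versus-modality contrasts, those differences are taken as constant, and a 1-point departure moves an estimate by about 0.4 points (live call 0.5). Report an arm-by-period check, and say that it has little power.

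The cost is SAP wording and one extra model; no further patients or data collection are needed. The Project Status section says no outcome data had been accessed when the file was posted, so a change made while that remains true would still be pre-specified.

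### The single 210-day malignancy window does not fit the Analysis 2.1 controls, who are defined as outreach-free for only 120 days, and the SAP states no other window for that comparison.

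*Combined protocol and SAP*

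**What the plan says.** Under Other Pre-specified Outcomes, the SAP opens with "We will run the analyses described above on the following additional outcomes". The confirmatory analyses above that line are Analysis 1 (live call against the other modalities, 180 days) and Analysis 2.1 (each modality against passive control, 120 days). Breast malignancy risk is item 2 on the list, with a single window: "Time Frame: In the 210 days following the outreach". Item 3, appointment scheduling, has "Time Frame: In the 30 days following the outreach".

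Analysis 2.1 takes its active patients from the first three waves. Its controls come from the "contemporaneous 120 days of the last 3 waves of outreach, during which outreach will not yet have occurred for those patients". The Methods section says that patients count as controls "during the span of time prior to which they are included in an active outreach arm", and gives an example of the pairing: "controls for patients in wave 2 will consist primarily of patients assigned to wave 6". For each control, "the starting date will be randomly chosen for each to match one of the treatment arms" (that is, the arms' send dates). The Design section describes "7 sequential waves of outreach occurring from May through November 2023".

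The Power Analysis section and the Primary Outcome paragraph both explain that follow-up lengths differ because suitable comparators are not always available.

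**The concern.** Read together, these sections apply a 210-day outcome to a comparison whose control group is defined by 120 days without outreach. For mammogram completion the plan recognises the limit and shortens the window from 180 to 120 days when the comparator is no outreach. It makes no such adjustment for malignancy.

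If 210 days is used for both groups, most controls will have had their own postcard, letter or call well before follow-up ends. The estimate would then no longer be the effect of outreach against none, which is what Question 2 asks. It would compare earlier with later outreach, and any effect of outreach would probably look smaller than it is. A null malignancy result against controls would be hard to interpret. If no window is fixed in advance, the choice falls to the analysis stage, between options that answer different questions.

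**Working it through.** **Inputs.**
- Malignancy window: 210 days (Other Pre-specified Outcomes, item 2).
- Outreach-free control time: 120 days (Analysis 2.1).
- Waves: 7, from May to November 2023 (Design); first outreach on 10 May 2023 (Methods).
- Pairing: first three waves with last three (Analysis 2.1), with wave 2 paired with wave 6 as the example (Methods). I take the pairs as 1-5, 2-6 and 3-7. The first and third are inferred from the example.

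**Formulas.** Outreach-free time for a control = date of own outreach minus assigned start date. Because the start date is matched to a send date in the paired active wave, this is the gap between the two waves. Days of follow-up after own outreach = 210 minus that gap.

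**Step 1: reproduce the plan's 120 days.** Assume monthly waves on the same day of the month.

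| Pair | Dates (2023) | Gap (days) | 210 - gap (days) |
|---|---|---|---|
| 1-5 | 10 May to 10 Sep | 123 | 87 |
| 2-6 | 10 Jun to 10 Oct | 122 | 88 |
| 3-7 | 10 Jul to 10 Nov | 123 | 87 |

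The gaps are just over 120 days, so the 120-day window in Analysis 2.1 agrees with the wave schedule. Under a 210-day window, 87/210 = 41% to 88/210 = 42% of follow-up for a control who is later contacted comes after that control's own outreach.

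**Step 2: drop the same-day assumption.** Keep one wave per calendar month, and take the earliest possible active date with the latest possible control date.

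| Pair | Dates (2023) | Longest gap (days) | 210 - gap (days) |
|---|---|---|---|
| 1-5 | 10 May to 30 Sep | 143 | 67 |
| 2-6 | 1 Jun to 31 Oct | 152 | 58 |
| 3-7 | 1 Jul to 30 Nov | 152 | 58 |

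Even in the most favourable case, at least 58 of the 210 days (28%) come after the control's own outreach. Outreach spread across a month can also make gaps shorter than nominal, which only increases the overlap.

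**Step 3: do the other uses of these windows work?** In Analysis 1 every patient has outreach at day 0, so 210 days raises no such problem. The 30-day scheduling window fits inside 120 days. The conflict is confined to malignancy against passive controls.

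**The case against.** The strongest reply is that Analysis 2.1 carries its own limit. The 120 days is part of how the control group is defined as well as a label on the outcome, so repeating that analysis on malignancy would bring 120 days with it for both groups. The plan's stated principle, that windows depend on available comparators, supports this. The reading is reasonable and stands as a possibility, but the SAP does not state it. The 30-day bracket on the scheduling outcome matches neither 180 nor 120 days, so a bracket in this list can replace an analysis window. Nothing limits the 210-day bracket to comparisons among active arms. The 30-day case does not settle the matter either way, because 30 days fits inside 120 and never tests the control limit.

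A second reply is that malignancy may not have been meant for Analysis 2.1. Item 1 under the same lead-in sets out its own regressions among active arms only, so the lead-in is not applied literally to every item. This has some weight and lowers confidence. Items 2 and 3, however, specify no regressions of their own and depend on the lead-in.

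A reader might also infer that active patients would be followed to day 210 and controls only to day 120. The documents do not support this: the control period is described as contemporaneous, and control start dates are matched to send dates, both of which point to equal follow-up.

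Finally, the Methods section adds to the control groups some patients who become ineligible before their own wave, and they may never be contacted. The overlap therefore applies to controls who are later contacted. The added patients supplement a group drawn mainly from the later waves. Since a completed mammogram is one route to ineligibility, they could not serve alone as the comparator.

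**Conclusion.** The point holds with moderate confidence. Applied as written, the 210-day window puts about 87-88 days of follow-up after the controls' own outreach, and at least 58 days, for controls who are later contacted. The first figure assumes same-day monthly spacing. The second assumes only one wave per calendar month. Both assume the 1-5, 2-6 and 3-7 pairing. The malignancy contrast would then be early versus delayed outreach, probably diluted. These figures count days of follow-up and do not measure bias; without a malignancy rate in the documents, the bias cannot be computed.

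A reader might conclude that the comparison cannot be run at all. That goes too far: the regression can be fitted, but its result could not be reported as outreach against no outreach. Nor does the point reach the main results. Malignancy is not labelled confirmatory, and the confirmatory mammogram analyses (1 and 2.1) use windows of their own.

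**What to change.** State the malignancy window separately for each comparison. Keep 210 days for the analyses between modalities. For Analysis 2.1, either use one window of at most 120 days from the start date, the same in active and control groups, or state that malignancy is not compared with passive controls.

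This takes one or two sentences in the SAP. The Project Status section reports that no outcome data had been accessed when the document was posted, so the wording can be settled before outcomes are seen, provided that is still the case. The price is fewer malignancy events in the control comparison under the shorter window, or loss of that comparison under the second option.
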